RESEARCH PROTOCOL

Official Title: Effects of AINurse Orientation Program on Psychological Outcomes and Length of Hospital Stay: A Randomized Controlled Trial

Date of the document: September 1, 2025

Method

Aim

This study aimed to develop a structured AINurse and Human Nurse orientation training program for intensive care unit (ICU) patients and compare the effects of these training programs on ICU patients' delirium-free days, level of anxiety and depression, and length of stay in the ICU.

Study Type and Design

This study is designed as a single-center, randomized controlled experimental study. The study trial protocol will be registered on clinicaltrials.gov . The Consolidated Standards of Reporting Trials (CONSORT) diagram will be used for reporting the study.

Hypotheses of the Study

H1: Patients who receive the structured AINurse patient orientation training program will have longer delirium-free days than patients who receive Human Nurse orientation training.

H2: Patients who receive the structured AINurse patient orientation training program will have lower levels of anxiety and depression than patients who receive the Human Nurse orientation training.

H3: Patients who receive the structured AINurse patient orientation training program will have shorter lengths of stay in the intensive care unit than patients who receive the Human Nurse orientation training.

Setting, Participants, and Sample Size

The study is planned to be conducted between July 2025 and July 2026 in the adult intensive care unit of Koç University Hospital, a tertiary care hospital in Türkiye. The general intensive care unit (GICU) of Koç University Hospital has 16 beds and the cardiovascular surgery intensive care unit (CVSICU) has eight beds. The hospital where the study will be conducted has a total of 1950 patient admissions annually, 1500 in the NICU, and 450 adult patients in the CVSICU. While the experimental group will receive the AI Nurse Orientation Training Program, the control group will receive the Human Nurse Orientation Training Program. Since there is no similar study to this study, a pilot study will be conducted with 10 patients. After the pilot study, the sample size will be calculated using G-Power.

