Phase 4: Implementation of structured orientation training to intervention and experimental group: In the experimental group, the structured AI-Nurse orientation program will be listened to twice daily (10:00 and 14:00) through a headset connected to a structured

audio recording application. The content will include orientation to time and environment but will exclude any personally identifiable information such as the patient's name. Following each orientation session, the daily news will be played with the help of the television in the patient's room (at 10:30-14:30), aiming to enhance environmental awareness and perception of real-time audio streaming. The TTS engines to be used will be able to provide real-time audio streaming. This intervention will be implemented by the same researcher over a three-day period. Anxiety and depression levels, as well as the CAM-ICU score, will be assessed both before and after the intervention. After three days of structured AI-Nurse training, the patient's discharge time from the ICU will be followed and recorded. In the control group, the structured orientation training will be given face-to-face by the Human-Nurse researcher. The patient in this group will also be monitored for signs and symptoms of delirium for three days. Anxiety and depression levels will be measured prior to the intervention, while post-intervention evaluations will include the number of delirium-free days, anxiety and depression scores, and length of stay in the ICU.

Data Collection Instruments

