Data collection will take place between July 2025 and July 2026. After obtaining written informed consent, randomization will be performed among patients hospitalized in the intensive care unit and the cardiovascular surgery intensive care unit who meet the inclusion criteria and voluntarily agree to participate in the study. In the first stage, patients' CAM-ICU form and RASS scores will be calculated. For patients who meet the inclusion criteria, the

sociodemographic characteristics form and clinical patient information form will be completed by the researchers. Patients in the intervention group included in the study will be given structured AI-Nurse orientation training starting at 10:00 am (approximately 10 minutes), and then the patient will listen to the daily morning news on television. At the end of the day, at 16:00, CAM-ICU and HADS will be evaluated. This process will continue with the same patient for three days. If the delirium score is between 3 and 7 points for three days and the RASS value is +4 belligerent, +3 very agitated, -2 slightly sedated, -3 moderately sedated, -4 deep sedation, -5 unstimulated, this training and follow-up process will be stopped, and the intervention will be ended. Patients assigned to the control group will fill in the same forms, and after the structured orientation training is given by the researcher (Human Nurse), the television will be turned on in the same way, and the daily news will be listened to. At the end of the day, CAM-ICU and HADS will be evaluated at 16:00. This practice will continue with the same patients for three days. After three days of follow-up, the length of stay of the patients in the intensive care unit will be monitored until discharge.

Data Analysis

Data will be analyzed using IBM SPSS Statistics, Version 28.0 (Armonk, NY: IBM Corp., 2021). Sociodemographic characteristics will be reported using descriptive statistics such as frequency, percentage, mean, and standard deviation. Descriptive statistics will be used to analyze the data. Whether the data are normally distributed will be evaluated with the Shapiro-Wilk test. The t-test will be used for normally distributed data. If the data are not normally distributed, the Mann-Whitney U test will be used.

Ethical Consideration

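### For H2 the protocol names only a t-test or Mann-Whitney U, with no adjustment for the pre-intervention HADS it plans to collect; ANCOVA would probably be more precise, and the data-collection schedule should list that HADS.

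*Protocol*

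**What the plan says.** H2 (Hypotheses of the Study) is that AINurse patients "will have lower levels of anxiety and depression than patients who receive the Human Nurse orientation training".

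Study Intervention, Phase 4, plans a baseline in both arms. For the AINurse arm: "Anxiety and depression levels, as well as the CAM-ICU score, will be assessed both before and after the intervention". For the control arm: "Anxiety and depression levels will be measured prior to the intervention", with anxiety and depression scores again among the post-intervention evaluations.

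Data Collection and Follow-up gives the sequence in practice. CAM-ICU and RASS come first; then the "sociodemographic characteristics form and clinical patient information form will be completed by the researchers"; then the training. HADS first appears after that day's training: "At the end of the day, at 16:00, CAM-ICU and HADS will be evaluated". This is repeated for three days, and the control arm follows the same pattern.

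Data Analysis checks normality with Shapiro-Wilk and then says: "The t-test will be used for normally distributed data. If the data are not normally distributed, the Mann-Whitney U test will be used". It does not say whether the variable tested is the post-intervention score or the change from baseline. It names no adjusted model.

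**The concern.** The trial intends to hold a baseline value of the very outcome that H2 compares, but the stated method makes no covariate adjustment for it. H2 speaks of levels, so the natural reading is a two-group comparison of post-intervention scores. If the same questionnaire, repeated in the same patient within about three days, is correlated with itself to any useful degree, that comparison gives a wider interval than the same data allow.

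The second issue is practical. A team working only from Data Collection and Follow-up would take the first HADS at 16:00 on day 1, after training had begun. A true baseline missed in this way cannot be recovered, and no baseline-using analysis would then be possible.

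**Working it through.** **Inputs.** The protocol states no N, alpha, power, effect size, SD or r; the sample size is to follow a 10-patient pilot. There is therefore no figure of its own to reproduce. Everything below is assumed: equal arms of n = 15, 30 or 64, normal scores, the same SD and slope in both arms, a two-sided 95% interval, and r from 0 to 0.7.

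**Step 1: the three candidate analyses.** With equal SDs before and after, the variance of the arm difference relative to final scores alone is, in large samples:
- final score: 1
- change score: 2(1 - r)
- ANCOVA: 1 - r²

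| r | Final | Change | ANCOVA |
|---|---|---|---|
| 0.3 | 1 | 1.40 | 0.91 |
| 0.5 | 1 | 1.00 | 0.75 |
| 0.7 | 1 | 0.60 | 0.51 |

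Since 2(1 - r) - (1 - r²) = (1 - r)², which is never negative, the change score is never more precise than ANCOVA. Since 2(1 - r) exceeds 1 when r < 0.5, it is then worse than ignoring the baseline.

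**Step 2: small-sample cost of ANCOVA.** Expected 95% half-widths, in SD units:
- t-test: t(0.975, 2n-2) × E[s; 2n-2 df] × √(2/n)
- ANCOVA: t(0.975, 2n-3) × E[s; 2n-3 df] × √(1 - r²) × E[√(2/n + D²/Sxx)], where D ~ N(0, 2/n) is the chance baseline difference and Sxx ~ chi-square(2n-2)

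The ratio of ANCOVA to t-test is k × √(1 - r²). At n = 15, taking √(2/n) out of both expressions, k = (2.0518 × 0.9908 × 1.0187) / (2.0484 × 0.9911) ≈ 1.020. At n = 30 and 64, k = 1.0091 and 1.0041.

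**Step 3: interval width against the final-score t-test.** Example: n = 15, r = 0.5 gives 1.020 × 0.866 = 0.883, which is 11.7% narrower.

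| r | 15 per arm | 30 per arm | 64 per arm |
|---|---|---|---|
| 0 | 2.0% wider | 0.9% wider | 0.4% wider |
| 0.1 | 1.5% wider | 0.4% wider | 0.1% narrower |
| 0.2 | 0.1% narrower | 1.1% narrower | 1.6% narrower |
| 0.3 | 2.7% narrower | 3.7% narrower | 4.2% narrower |
| 0.5 | 11.7% narrower | 12.6% narrower | 13.0% narrower |
| 0.7 | 27.2% narrower | 27.9% narrower | 28.3% narrower |

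The break-even correlation is r = √(1 - 1/k²), about 0.20, 0.13 and 0.09 at 15, 30 and 64 per arm.

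**Step 4: the same thing in patients (illustration only).** For a 0.5 SD difference, 80% power and two-sided 5%, the unadjusted t-test needs 64 per arm. ANCOVA (noncentral t, 2n-3 df, variance (1 - r²)(1 + 1/(2n - 4))) needs 65, 64, 62, 59, 49 and 34 per arm at r = 0, 0.1, 0.2, 0.3, 0.5 and 0.7.

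**Step 5: the two schedules side by side.** Phase 4 has a pre-intervention HADS in both arms; Data Collection and Follow-up does not list one. The latter also leaves out the 14:00 session given in Phase 4, so it reads as an abbreviated account and not as a competing design.

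**The case against.** **This is a preference about efficiency, and covariates belong in an SAP.** Data Analysis is short and generic, and a separate SAP may name an adjusted model. That would dispose of the point if the protocol were silent. It is not: it names the comparison, and an SAP that adjusted for baseline would depart from that text. It is true, however, that the tests are named for all data and not assigned specifically to H2.

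**The size is wholly assumed.** This stands. Nothing in the protocol locates r, and the grid runs from 2.0% wider to 28.3% narrower. It also assumes normal scores, while the protocol provides for non-normal ones. The case rests on the asymmetry: a small, bounded loss against a potentially substantial gain.

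**Stronger readings that the protocol does not support:**
- A reader might infer that the named tests *cannot* use the baseline. Either test can be run on change from baseline, and Data Analysis does not say which variable is tested.
- A reader might infer bias or invalidity. Under randomisation the unadjusted comparison is valid.
- A reader might infer that the design has no baseline HADS, or that the two sections contradict each other. Phase 4 plans it in both arms; the later section merely omits it.
- A reader might infer from the provision that "this training and follow-up process will be stopped, and the intervention will be ended" that many day-3 scores will be missing. That rule is worded around a raised delirium score for three days together with listed RASS values. Taken literally, it is met only once three days have passed, so it does not show patients with earlier scores but none on day 3. Free withdrawal, under Ethical Consideration, is the better-supported source of missing scores, and its extent is unknown.

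**Conclusion.** The point holds as one of precision, worth acting on before the sample size is calculated. The named tests either ignore the planned baseline or, on change scores, use it no more efficiently than ANCOVA, given equal SDs and apart from the negligible small-sample cost. ANCOVA gains whenever r exceeds roughly 0.1 to 0.2, depending on arm size. A lower correlation between repeats of one questionnaire over about three days would be surprising, but that is a judgement and not a figure from the protocol. The percentages depend on the assumed r, arm sizes, normality and common slope, so they show a range and do not estimate the gain in this trial.

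The missing line in Data Collection and Follow-up is an editorial gap, but following that section alone would lose the baseline for good.

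**What to change.** **Data Analysis.** For H2, compare each HADS subscale after the intervention (for example at 16:00 on day 3) between arms by ANCOVA, with the pre-intervention score of the same subscale as covariate, and report the adjusted difference with its 95% CI. Keep the t-test or Mann-Whitney U as a sensitivity analysis, which retains the provision for non-normal data, and state whether it uses final or change scores.

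**Optional.** If day-3 scores are missing, for example through withdrawal, a mixed model of the day 1-3 scores with the same baseline covariate keeps patients who have earlier scores. State its missing-at-random assumption. The point does not depend on this.

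**Data Collection and Follow-up.** List HADS among the assessments before the first session in both arms, to match Phase 4.

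**Cost.** One or two sentences and one line. No measurement is added, because Phase 4 already plans the baseline, and the named software fits these models. The statistical cost at r = 0 is the 2.0% (15 per arm) to 0.4% (64 per arm) widening shown above.
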